10.3 Data management

Clinical data will be collected using Open Data Kit (ODK [<https://opendatakit.org>]) and Android devices. Electronic data entry quality will be ensured by real-time error capture, internal validation, consistency checks and stringent formatting constraints. Completed data forms will be securely transferred by direct internet connection to a 256 bit SSL encrypted and fire-walled ODK server, which is hosted at LSHTM (www.odk.lshtm.ac.uk). Data connections with the encrypted server can be made over mobile connections and data are transferred automatically to the server whenever an internet access point is available. This allows continuous backup of data and quality monitoring in real time.

Data from each site will be accessible to investigators responsible for that site throughout the study. Anonymised quantitative data will be held for sharing as original databases stored with a soft copy of the fully annotated questionnaires and the STATA scripts files used for recoding and analysis. Personal identifiers, such as names, will not be held, with ID numbers used instead. Details of how to access the data will be published with each study publication, and will be provided to any *bona fide* researcher requesting access. The LSHTM Data Compass repository will also enable access to repository contents through a searchable index.

The qualitative data will be made available in second-order formats to protect the confidentiality of participants. Making full interview transcripts or fully transcribed field notes publicly available would risk participant identification and could hamper participation in the study. Second-order summaries of both the observational data and interviews will be prepared in the form of daily contact summaries that are anonymised and therefore sharable. This process will be described to participants at the point of consent.

The LSHTM Research Data Management Support Service, through the LSHTM institutional Research Data Repository, will store off-site backups indefinitely. Microorganism isolates, DBS, residual frozen blood and serum samples, and residual pharyngeal samples will be archived at LSHTM, providing that there is institutional support to maintain quality management systems for archiving and retrieval, power backup and -80°C freezer capacity.

10.4 Immediate and long-term use of the data

Data collected in this study will be compiled, analysed, and made available to collaborating partners and to ministries of health in participating countries, and will be prepared for publication in open-access peer-reviewed journals. Data may be made available to research students in participating countries and at participating institutions for educational use. The investigators will comply with international standards and guidelines regarding open access to research data. Study protocols, SOPs and data collection tools will be made freely available on a dedicated study website. Upon completion of the study, all study documents and record forms will be filed and stored at study sites for at least 10 years. Electronic data records will be stored indefinitely by investigator/s in research facility systems. Results of the study may be publicized in the future by collaborating partners and stakeholders as part of public health education efforts and control programs for infectious diseases and use of antimicrobial medicines (see also section 14).

11 DATA ANALYSIS AND STATISTICAL CONSIDERATIONS

Quantitative data analysis will be performed with Stata and other software packages.

11.1 Quantitative outcome measures and analysis

Listed by study objective:

- 1) To determine the treatable and/or preventable causes of fever in children and adults presenting as outpatients, and among those admitted to hospitals, in areas represented by the study sites;

For outpatients the attributable fraction (AF) will be calculated for each pathogen or group of pathogens. This will be done separately for each site and age stratum. For each group of patients, the odds ratio (OR) for the association between each pathogen and fever will be calculated by comparing cases and controls. Logistic regression will be used to calculate the odds ratio. In order to take the matched design into account, strata based on geographical location and season will be defined at each site and the analysis will be adjusted for age, sex and stratum. Since cases and controls are recruited at a constant rate throughout the year but fever incidence is likely to vary by season, the analysis will be weighted by the proportion of patients included in the study of the total number of cases seen at the study

site in the given season. AF will then be calculated as $AF_A = p_A(1-OR_A)$. Confidence intervals will be calculated in an appropriate way, e.g. bootstrapping or delta method.

For inpatients, first the distribution of diagnoses in each site will be tabulated for all inpatients in the study. Then a second analysis to calculate AFs will be carried out for inpatients, but this will be restricted to inpatients who come from the same geographical area as the controls. The calculation of AFs for inpatients may be dropped if insufficient numbers of in-patients come from the same area as the controls.

- 2) To determine how fever aetiology varies according to patient age, level of the health system, geographical area, local malaria and HIV prevalence, and other risk factors;

Stratified analyses will be carried out as above to estimate the AF for sub-groups of patients.

- 3) To determine the prevalence and spectrum of antimicrobial resistance among bacterial pathogens identified in clinical specimens from febrile patients;

At each site the proportion of bacterial pathogens with antimicrobial resistance defined by standardized criteria will be calculated. The proportion of common organisms demonstrating resistance to a standard panel of antibiotics will be reported.

Specific secondary objectives:

1) To generate data on incidence of specific infections among study participants, and therefore contribute key data on disease burden for some infections that are not counted in current “global burden of disease” estimates;

For an area whose population size is known, a health utilization survey will be used to estimate r , the proportion of fevers for which treatment was sought at a study centre. The total number of cases seen at the study site from the defined population will be multiplied by $1/r$, to obtain the total cases in a year from the defined population. This will be divided by the size of the population to estimate incidence. Incidence of fever caused by specific pathogens will be calculated by multiplying the incidence by the AF for that pathogen.

3) Evaluation of available biomarker assays to assess their performance and potential utility in fever case management in the study areas;

The sensitivity, specificity, and positive and negative predictive value of each biomarker will be estimated.

4) To generate data to support the development of new fever case management algorithms which may be evaluated in future studies;

The association between the presence of pathogens with predefined clinical and other variables will be examined.

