11.2 Sample size considerations

Any single pathogen or aetiology is assumed to be likely to be rare in the study populations.^{2,14,15} To identify causes of fever, a sample size of 600 patients per group will enable estimation of the prevalence of an infection whose true prevalence is 5% with a precision of +/- 1.7% with 95% confidence, and to estimate the prevalence of an infection whose true prevalence is 1% with a precision of +/- 0.8% (see Table 3).

Table 3. Sample size estimates for varied infection prevalences

Number of participants	Prevalence	Confidence interval
600	5%	+/- 1.7
600	2%	+/- 1.1
600	1%	+/- 0.7

Since blood cultures and convalescent samples will not be taken from community controls, the prevalence of respiratory viruses (e.g., influenza and RSV) detected by polymerase chain reaction (PCR), and of baseline seropositivity to other pathogens, will be compared in cases and controls. The prevalence of respiratory viruses, and of seropositivity to common causes of fever, is assumed to be approximately 5% in the general population. A sample of 600 outpatients and 300 controls will provide >90% power to show a significant difference between a prevalence of 12% in cases and 5% in controls. Therefore, 600 febrile patients will be enrolled in each of four analysis groups (children aged ≥ 2 months to <15 years as inpatients and outpatients, and inpatients and outpatients aged ≥ 15 years), for a total of 2400 patients per site; plus 300 controls in each of the two age groups at each site (total 600).

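### For pathogens carried by fewer than about 0.5–1% of controls, often none of the 300 controls per stratum is positive; the logistic-regression OR is then infinite and neither interval method named in Section 11.1 works

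*Protocol*

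**What the plan says.** Protocol Section 11.1, primary objective 1: "For outpatients the attributable fraction (AF) will be calculated for each pathogen or group of pathogens", and "This will be done separately for each site and age stratum". With five sites and two age groups this makes ten outpatient analyses per pathogen. On the estimator: "Logistic regression will be used to calculate the odds ratio", and "the analysis will be adjusted for age, sex and stratum", the strata being location and season. The analysis is also weighted by the share of each season's patients who were enrolled. On intervals: "Confidence intervals will be calculated in an appropriate way, e.g. bootstrapping or delta method".

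Section 11.2 states: "Any single pathogen or aetiology is assumed to be likely to be rare in the study populations". Its Table 3 plans precision in patients for prevalences of 5%, 2% and 1%. It sets 600 patients per analysis group and 300 controls per age group at each site. The only control prevalence it gives is about 5%, for respiratory viruses and for seropositivity to common causes.

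Under Section 7.5.3 controls have the same tests as patients, apart from blood culture, convalescent serum and urine. Section 7.6.2 has smears from patients and controls read for *Borrelia* and non-malaria blood parasites as well as malaria. Rare agents with little background carriage are therefore within the case-control comparison.

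**The concern.** A pathogen that is rare in patients and strongly linked to fever is rarer still in healthy controls. With 300 controls, a count of zero is then a likely result, and a maximum-likelihood logistic fit has no finite OR for it. At a given prevalence in cases, the chance of this rises with the strength of the association, so the method gives way where the evidence of causation is best. Section 11.1 carries the AF into the incidence estimates of secondary objective 1, and objective 2 repeats the analysis in smaller sub-groups, where control counts are lower still. The only fallback in 11.1 concerns inpatients from outside the controls' area. It does not cover a pathogen absent in controls.

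**Working it through.** **1. The plan's own figure.** Inputs from Section 11.2: 12% of 600 cases against 5% of 300 controls; two-sided alpha 0.05 is assumed, as none is stated. Pooled prevalence = (72 + 15)/900 = 0.0967. Standard error under the null = √(0.0967 × 0.9033 × (1/600 + 1/300)) = 0.0209; under the alternative = √(0.12 × 0.88/600 + 0.05 × 0.95/300) = 0.0183. Power = Φ((0.07 − 1.96 × 0.0209)/0.0183) = 94.4%. The stated power above 90% is correct. It concerns an agent at 5% in controls.

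**2. Chance of no positive control.** P₀ = (1 − q)ⁿ, with q the control prevalence. Except for 5%, the values of q are assumptions.

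| q | n = 300 | n = 600 |
|---|---|---|
| 5% | 0.00002% | about 0 |
| 1% | 4.9% | 0.2% |
| 0.5% | 22% | 4.9% |
| 0.2% | 55% | 30% |
| 0.1% | 74% | 55% |

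The 600 column is the largest control group allowed by Section 7.5.1, one control per outpatient where a site has capacity. The chance that at least one of ten strata has no positive control, 1 − (1 − P₀)¹⁰ at n = 300, is 40% for q = 1% and 92% for q = 0.5%.

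**3. The same in terms of case prevalence.** With case prevalence p from Table 3 and an assumed true OR, the control odds are p/(1 − p)/OR. P₀ for 300 controls:

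| p | OR 2.6 | OR 5 | OR 10 | OR 20 |
|---|---|---|---|---|
| 1% | 31% | 55% | 74% | 86% |
| 2% | 9.6% | 29% | 54% | 74% |
| 5% | 0.2% | 4% | 21% | 46% |

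The OR of 2.6 is the protocol's own contrast: (0.12/0.88)/(0.05/0.95) = 2.59.

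**4. What happens at zero.** Take 12/600 cases and 0/300 controls, unadjusted.

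- Maximum likelihood: the OR is about 37,000 after 10 iterations, and the fit then stops on a singular matrix. This is quasi-complete separation, since pathogen-negative people include both cases and controls.
- Delta method: no finite variance exists.
- Bootstrap: resampling 0/300 always returns 0/300. Even with one positive control, (299/300)³⁰⁰ = 37% of resamples have none.
- Firth: OR = (12.5 × 300.5)/(588.5 × 0.5) = 12.8, with a profile-likelihood lower limit of 1.67.

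**5. Effect on the AF.** This uses AF = p(1 − 1/OR). As OR goes to infinity, AF goes to p = 2.0%. The Firth estimate gives 0.02 × (1 − 1/12.8) = 1.84%, and its lower limit gives 0.02 × (1 − 1/1.67) = 0.8%. A second route agrees: the upper 97.5% limit for 0/300 is 1 − 0.025^(1/300) = 1.22%, and without adjustment AF = (p − q)/(1 − q) = (0.02 − 0.0122)/0.9878 = 0.8%.

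Both 0.8% figures hold p at 2%. A bootstrap does vary p, by about ±1.12 points, and so gives roughly 0.9% to 3.1%, but nothing for the background. Adding the two errors in quadrature as a rough guide, √(1.12² + 1.22²) = 1.66 points, puts the lower limit near 0.3%.

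**The case against.** The strongest reply is that the protocol does not prescribe maximum likelihood. It says only logistic regression, a term that covers exact and Firth fits, and its interval sentence gives examples without binding anyone. Zero-cell handling could sit in an analysis plan that is not shown. This stands in part: a reader might infer that the protocol forces a failing method, and its wording does not. But it names an estimator, a level of stratification and two interval methods, and at zero the usual fit and both named intervals fail.

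A reader might also infer that zero counts will be common across pathogens. The documents do not support that. At 5% in controls the problem is absent, and at the protocol's own contrast (OR 2.6) it is 0.2%, 9.6% or 31% for case prevalences of 5%, 2% and 1%. No control prevalence is given for rarer agents.

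A third tempting inference is that the primary measure cannot be computed at all. That goes too far, because p(1 − 1/OR) has the finite limit p. What fails is the OR and an honest interval.

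Grouping pathogens, which 11.1 allows, and recruiting more controls both help. With 600 controls, p = 2% and OR 10, the chance still stands at 29%.

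**Conclusion.** The concern holds for pathogens that are tested in controls and carried by fewer than about 0.5–1% of them. There the chance that a stratum has no positive control runs from about 5% (q = 1%) to 74% (q = 0.1%) with 300 controls. When it happens, maximum likelihood gives no OR, the delta method gives no interval, and the bootstrap gives one that omits the background. In the worked example the lower limit would be about 0.9% where roughly 0.3% is warranted.

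The conclusion rests on assumed control prevalences and ORs, on unadjusted tables, and on the AF form p(1 − 1/OR). Section 11.1 prints p(1 − OR), which is a separate error and would run to minus infinity here. Diagnoses by blood culture, urine culture or convalescent serum are outside this point, because controls are not tested for them. The change should be made before the data are seen, but the point does not undermine the design.

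**What to change.** In Section 11.1, add a rule for any pathogen-stratum with a sparse cell, for example fewer than 5 positive cases or controls:

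- Estimate the OR by Firth-penalised logistic regression with the same covariates and profile-likelihood limits.
- Carry those limits and the sampling uncertainty in p into the AF interval.
- Do not use the delta method or a simple bootstrap in these cells.
- Deal with the seasonal weights explicitly. Profile and exact limits do not hold directly under sampling weights, so either adjust for season as a covariate in these cells or state how the weights enter the penalised fit.
- State how the AF and its interval are reported when no control is positive.

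The cost is a few sentences and standard software. The statistical price is slight shrinkage of large ORs towards 1 (in the example, an AF of 1.84% against 2.0%) and wider intervals in sparse strata, which reflect what 300 controls can show.

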6 STUDY POPULATION AND SELECTION CRITERIA

Participants will be patients who present with fever for health care at the selected health care facilities. Patients of all ages two months and older will be eligible for enrolment. Study sites include outpatient and inpatient facilities in Laos, Malawi, Mozambique, Myanmar, and Zimbabwe. Patients will be recruited if they fulfil all of the following criteria (see also section 7.2 on participant enrolment, and Screening and Enrolment Forms [Appendix C]):

- 1) Tympanic or axillary temperature $\geq 37.5^{\circ}\text{C}$ at presentation;
- 2) Not having been hospitalized or having undergone surgery in the previous month;
- 3) Age ≥ 2 months (two months or older);
- 4) For outpatients, residence (at the time of enrolment) within the defined catchment area around the health facility (see section 7.5.1);
- 5) For outpatients aged ≥ 15 years, absence of symptoms of lower respiratory infection and of diarrhoeal diseases as defined by:
 - a) cough AND ≥ 1 of the following: cough productive of green/yellow sputum, or haemoptysis;
 - b) ≥ 3 loose stools within the previous 24 hours;
- 6) For outpatients aged ≥ 2 months to < 15 years, absence of symptoms of diarrhoeal diseases as defined by: ≥ 3 loose stools within the previous 24 hours;
- 7) Willingness and ability to provide demographic and clinical information, and clinical samples, at the time of enrolment and 28 days later;
- 8) Provision of written informed consent for adult participants; or for children, provision of written consent from a parent/guardian and assent from the child (according to local regulations and practices at each study site).

Controls will be community members in the study site health facilities' catchment areas, frequency matched to participants by age and season (see section 7.5 for details of selection and study activities for community controls).

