7.5 Community controls

Interpreting the results of some serological assays and pharyngeal swab assays requires knowledge of background prevalence of infection or colonization in the study population. To address this, 600 community controls (section 11.3 sample size calculations), frequency matched by age, sex, month of enrolment (to address seasonality), and geographical area to the cases, will be selected from the community living in the catchment area of the health facility for each site. No controls will be specifically recruited for the inpatient population, who may come from a wider geographic area. However, an analysis comparing controls with our sample of in-patients who do come from the area from which controls were selected, will be carried out.

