7.5.1 Selection and recruitment of community controls

To define the catchment area for outpatients and community controls, existing data and pilot data from each site will be combined to define an area around the study facility in which approximately 80% of outpatients live. Residing within this area will be a selection criterion for FIEBRE outpatients (section 6). Community controls will be recruited within this area, individually matched to participating outpatients.

During each month of the study at each site, half of the outpatients will be selected at random (or by taking every second outpatient in chronological order of presentation). For each of these a community control will be found matched on age (within bands: ≥ 2 to < 6 months, ≥ 6 to < 12 months, ≥ 1 to < 3 years, ≥ 3 to < 5 years, in 5 year bands up to age 24, and in 10 year bands at older ages), sex and place of residence. At sites where the study team's capacity enables them to recruit a larger number of controls, controls will be matched to a larger proportion of enrolled outpatients. For example, if capacity allows, one control will be found for every outpatient; or controls will be found for more than half of the outpatients, e.g. for a random sample of three-quarters of enrolled outpatients (or by selecting every second, third, and fourth outpatient, in chronological order of presentation). This approach will allow us to enhance the precision of estimates for specific primary objective 1 and specific secondary objective 1 (see also section 11.1 below on quantitative outcome measures and analysis).

Community controls will be recruited and enrolled if they, or their parents/guardians, provide informed consent.

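### Controls are selected by calendar month, but the AF model adjusts for undefined seasons, which can understate the AF of sharply epidemic pathogens

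*Protocol*

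**What the plan says.** The protocol describes control selection in three places.

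- Section 6: controls are "frequency matched to participants by age and season".
- Section 7.5: controls are "frequency matched by age, sex, month of enrolment (to address seasonality), and geographical area to the cases".
- Section 7.5.1: controls are "individually matched to participating outpatients". The procedure runs by month ("During each month of the study at each site, half of the outpatients will be selected at random"), and each selected outpatient gets one control of the same age band, sex and place of residence.

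Section 11.1 (primary objective 1) estimates the odds ratio for each pathogen by logistic regression, separately by site and age stratum. To reflect the matching, "strata based on geographical location and season will be defined at each site and the analysis will be adjusted for age, sex and stratum". Neither the length of a season nor the form of the age term is given. The same section explains its weighting by season: "Since cases and controls are recruited at a constant rate throughout the year but fever incidence is likely to vary by season". The odds ratio feeds the AF, and under secondary objective 1 the AF multiplies fever incidence to give cause-specific incidence.

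**The concern.** Logistic regression with ordinary covariates is valid after matching on discrete factors, provided that it adjusts for those factors at the level at which they were matched. Section 7.5 names month as its means of handling seasonality, and section 7.5.1 works by month, yet the model carries time only as season. If a pathogen comes and goes within a season, the coarser term mixes months with very different prevalence, and the common odds ratio moves towards 1.

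The AF is the primary outcome for outpatients, and a relative understatement of it passes unchanged into incidence. The pathogens most exposed are those with short epidemic peaks. Section 11.2 names influenza and RSV among the infections that rest on the case-control comparison.

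**Working it through.** **The plan's own figure.** Section 11.2 makes the following claim, where the second prevalence, that of the controls, is 5%: "A sample of 600 outpatients and 300 controls will provide >90% power to show a significant difference between a prevalence of 12% in cases and". Two-sided alpha of 0.05 is assumed, since none is stated there.

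- Pooled prevalence = (72 + 15)/900 = 9.67%.
- Null SE = √(0.0967 × 0.9033 × (1/600 + 1/300)) = 2.09 points.
- Alternative SE = √(0.12 × 0.88/600 + 0.05 × 0.95/300) = 1.83 points.
- Power = Φ((7 − 1.96 × 2.09)/1.83) = 94.4%, which agrees with the protocol.
- The 95% half-width of the difference is 1.96 × 1.83 = 3.6 points. This is the yardstick for the bias below.

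**Set-up.** Six hundred cases and 300 controls at a constant rate give 50 cases and 25 controls per month. The fits are logistic regressions on expected counts, unweighted. AF is taken as p(1 − 1/OR), because the printed form p(1 − OR) is negative for any OR above 1; that is a separate matter. The protocol gives no seasonal curve, so every shape below is an assumption.

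**Four-month epidemic.** Background prevalence is 5, 20, 20, 5% in the epidemic months and 0.2% otherwise. The AF is 10, 35, 35, 10% in those months and zero otherwise. Case prevalence in a month is AF + (1 − AF) × background: 14.5, 48, 48, 14.5%, and 0.2% otherwise.

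- True AF = 90%/12 = 7.50%.
- Mean case prevalence = (14.5 + 48 + 48 + 14.5 + 8 × 0.2)/12 = 10.55%.
- Mean background = (50 + 1.6)/12 = 4.30%.

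| Time term | OR | AF = 10.55% × (1 − 1/OR) | Relative loss |
|---|---|---|---|
| Calendar month | 3.46 | 7.50% | none |
| Six-month seasons, peak inside one season | 2.83 | 6.82% | 9% |
| Three-month seasons, peak split across a boundary | 2.83 | 6.82% | 9% |
| Six-month seasons, peak split across the boundary | 2.62 | 6.53% | 13% |

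The last row can be checked by hand. Both seasons then have the same prevalences, so the adjusted OR equals the crude one: (0.1055/0.8945)/(0.0430/0.9570) = 2.62. If three-month seasons happen to hold both peak months together, the OR is 3.18 and the AF 10.55% × (1 − 1/3.18) = 7.23%, a loss of about 4%.

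**Protocol prevalences.** With 12% in cases, 5% in controls, a constant within-month OR and 90% of control positives in two months of one quarter:

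- month strata: OR 4.06, AF 9.05%;
- three-month strata: OR 3.21, AF 8.27%, a loss of (9.05 − 8.27)/9.05 = 9%;
- six-month strata: OR 2.75, AF 7.64%, a loss of 16%.

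**Where the loss is small or absent.**

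- No seasonality, 12% v 5%: AF 7.37% with every time term.
- Three peak months that coincide with one three-month season: AF 7.87% with either three-month or month strata.
- 5% v 2%, 90% of control positives in two months: 3.32% (month) against 3.21% or 3.11%, a loss of 3% to 6%.
- Rare pathogen, background peak 4% and AF peak 10%: 2.30% (month) against 2.25% (six-month), a loss of 2%.

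**When the direction holds.** With no effective time adjustment and a constant case:control ratio, p(1 − 1/OR) equals mean AF − cov(AF, background)/(1 − mean background). In the epidemic above, cov = (2 × 0.10 × 0.05 + 2 × 0.35 × 0.20)/12 − 0.075 × 0.043 = 0.00928. The loss is therefore 0.00928/0.957 = 0.97 points, and 7.50 − 0.97 = 6.53%, as in the table. The loss arises because AF and background rise together. If the true AF were 7% in every month, six-month strata split by the peak would return 7.00% and month strata 7.22%.

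**The case against.** Several points on the other side stand.

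- A reader might infer that the model adjusts for season alone. It does not: age, sex and location are in it too. The gap is confined to the time unit. The form of the age term is simply open, and no loss from the age bands has been shown.
- Season is undefined. Section 7.5 treats month as the seasonality variable, so the strata in section 11.1 could be months, in which case nothing is mismatched. Stratum width might also be set in an analysis plan that is not shown. However, section 11.1 already names a unit, and that unit differs from the one in sections 7.5 and 7.5.1, so the protocol should settle it.
- A reader might infer that any seasonal pathogen is biased. The constant-AF example shows otherwise: there the season strata are right and the month strata slightly high.
- The epidemics are assumed, and section 11.2 expects any single pathogen to be rare. The fits also omit the planned seasonal weights. Those weights are set by season and so cannot restore contrasts between months within a season, but they would change the figures.
- A reader might infer that the frequency and individual descriptions call for different models. They do not, because a model that adjusts for the matched factors serves both. Section 6 is also a summary that refers to section 7.5 for detail.

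**Conclusion.** The point holds in a limited form. Controls are drawn by month, while the AF model carries time as season, which on its ordinary reading is coarser. When background prevalence and AF peak together inside a season or across a season boundary, the AF is understated. The relative loss is roughly 9% to 13% in the assumed four-month epidemic, less if the strata happen to isolate the peak, and about 2% for a rare pathogen. It is nil without seasonality or if season means calendar month.

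In the four-month epidemic the absolute loss is 0.7 to 1.0 percentage points, well inside the half-width of about 3.6 points for one site and age group. When the AF and background peak together it runs in one direction, so larger numbers would not remove it. The sizes rest on assumed seasonal shapes and unweighted fits. No bias from age adjustment is claimed, and the inconsistent matching descriptions are a matter of wording. This is a worthwhile refinement and does not threaten the design.

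**What to change.** In section 11.1, make the time term calendar month of enrolment, alongside location, age and sex. Where positives are too sparse for monthly terms, use a smooth term in enrolment date. Keep season strata, with season defined, as a sensitivity analysis.

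As a secondary wording change, use one description of the matching (age band, sex, place of residence, calendar month) in sections 6, 7.5 and 7.5.1.

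The cost is about ten more model terms and some text, with no new data or participants. The loss of precision is negligible: in a simulated epidemic the standard deviation of the AF estimate was 1.63 points with month terms against 1.59 without them, and there was no difference when prevalence was flat over the year.
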